9.4.3 Safety

9.4.3.1 Adverse Events

For all safety analyses, the FAS (which is identical to the safety set) will be used.

The overall observation period will be divided into 3 mutually exclusive segments:

- 1. Pretreatment period: from day of subject's informed consent to the day before first dose of trial medication
- 2. On-treatment period: from day of first dose of trial medication to 30 days after last dose of trial medication
- 3. Posttreatment period: starts when the on-treatment period ends

Summary tables for AEs will include only AEs that started or preexisting AEs that worsened during the on-treatment period (ie, TEAEs).

The incidence of TEAEs (new or worsening from baseline) will be summarized by system organ class and/or preferred term; intensity (based on grades of NCI-CTCAE version 5.0) (see Section 8.4.1); type of AE; relationship to each trial treatment.

SAEs, nonserious AEs, and AESIs during the on-treatment period will be tabulated.

All deaths (on-treatment and posttreatment) will be summarized.

All AEs, fatal AEs, AESIs, and SAEs (including those from the pre- and posttreatment periods) will be listed and those collected during the pretreatment and posttreatment period will be flagged.

Further summaries of AEs will be specified in the SAP.

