2.3.2 Potential Risks

2.3.2.1 Potential Risks of GEN1053

The nonclinical studies performed with GEN1053 demonstrated thrombocytopenia, bleeding, anemia, and increased plasma levels of ALT, AST, and LDH with delayed onset in monkeys. The exact MoA has not yet been determined. However, there was no cytokine release, hemocompatibility issues, or direct binding of GEN1053 to human or cynomolgus monkey platelets and erythrocytes detected. Possible mechanisms could be platelet aggregation caused by

GEN1053-induced ADAs that were rapidly cleared due to immune complex formation and thus not detected, or CD27-related exaggerated pharmacology affecting the lymphoid cells and bone marrow function at the high dose levels employed in the monkey studies. Overall, based on the observed toxicities in monkeys, additional safety measures will be taken when exploring GEN1053 in the first clinical trial.

A mitigation plan for handling AEs, including elevated liver parameters, CRS, IRRs, and thrombocytopenia, related to the trial treatment has been prepared for this trial to closely monitor for and ensure dose delay, dose reduction, or withdrawal of subjects based on AEs that may occur during trial treatment (Section 6.7.2).

Risk mitigation strategies are provided in Section 6.7.2 and summarized in Section 2.3.3.

Targeting CD27 has not in itself led to unacceptable toxicities or safety concerns with other compounds in clinical development (see Section 2.2.4.2).

Potential subjects will be fully informed of the risks and requirements of the trial, and during the trial, subjects will be given any new information that may affect their decision to continue participation. They will be told that their consent to participate in the trial is voluntary and may be withdrawn at any time with no reason given and without penalty or loss of benefits to which they would otherwise be entitled. Only subjects who are fully able to understand the risks, benefits, and potential AEs of the trial and provide their consent voluntarily will be enrolled.

GCT1053-01 phase 1a data showed an increased frequency of severe cytopenias and severe transaminase increases in subjects treated with GEN1053 with prior anti-PD-1/PD-L1 exposure within the last 6 months. Due to this potential risk subjects treated with anti-PD-1/PD-L1 within the last 6 months are excluded from participation in the trial.

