6.7.2 Dosing Modification Guidance and Stopping Criteria

6.7.2.1 Dose Delays and Interruptions for GEN1053 or GEN1053+IM

The methodology for dose escalation is provided in Sections 4.2.1 and 4.2.2.

No intrasubject dose de-escalation will be allowed. The doses of GEN1053 or IM cannot be reduced but may be delayed.

- Administration of trial treatment can be delayed for up to 21 days (ie, 1 cycle) unless otherwise approved by the sponsor medical monitor. If the severity resolves to ≤ grade 1 or baseline within this period, retreatment may be considered under the following conditions:
 - In case of safety concerns, and for subjects who experience a recurrence of the same AEs of < grade 3 severity with rechallenge of GEN1053 or GEN1053+IM, a consultation between the sponsor and investigator will occur to determine whether the subject should continue trial treatment at the same schedule or whether the dosing interval in subsequent cycles should be increased. The sponsor may also consult the DMC as specified in Appendix 1.
 - A subject who experiences the same AE of \geq grade 3 with rechallenge of GEN1053 or GEN1053+IM must discontinue trial treatment immediately.
- For subjects receiving GEN1053+IM combination therapy, both GEN1053 and IM should be withheld or discontinued. Subjects may only continue GEN1053 or IM monotherapy if approved by the sponsor.

Decisions regarding dosing modification of trial treatment should be made using clinical judgment, considering relatedness of the AE to the trial treatment and the subject's underlying condition. For guidance, please see Table 6-2. The investigators are encouraged to contact sponsor in case of any safety concern that needs thorough discussion and evaluation.

Note that specific rules apply for irAEs, thrombocytopenia, neutropenia, CRS, and IRRs (see Sections 6.7.2.2 and 6.7.2.3).

Table 6-2 Dosing Modification and Management of Treatment-Related AEs

CTCAE Grade/Severity	Hold Treatment (Y/N)	Dosing Modification
Grade 1 or Grade 2 (Mild or moderate)	Ν	Continue treatment at the discretion of the investigator. If thrombocytopenia \geq grade 2 is identified, with or without bleeding, further treatment should be interrupted (see Section 6.7.2.3).
Grade 3 (Severe)	Y	Withhold treatment until resolution to \leq grade 1 or baseline
Grade 4 (Life-Threatening)	Y	Permanent discontinuation except if approved by medical monitor. If continuing on treatment, toxicity must resolve to grade 1 or baseline.

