7.1.1 Safety Follow-up Evaluation

Subjects discontinuing from treatment for any reason will have 2 safety follow-up visits, at 30 days (+5 days) and 60 days (\pm 7 days) after the last trial treatment administration, respectively. If the subject initiates new anticancer treatment within 30 days of the last trial treatment administration, the safety follow-up visit should be performed prior to starting new anticancer treatment. Once new anticancer treatment is initiated, the subject will move into survival status follow-up (see Section 7.1.2).

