8.4.2 Adverse Event Reporting

As noted in Section 8.1.3, medical conditions (signs, symptoms, and diagnosis) that occur after the ICF is signed and prior to the first dose should only be reported as AEs if they were assessed by the investigator to be caused by a protocol-mandated procedure (ie, tumor biopsy and/or CT scan), including wash-out or discontinuation of prior medications.

All other AEs, whether serious or nonserious (see definitions in Appendix 3), will be documented from the first dose of trial treatment until the last safety follow-up visit, subject withdrew consent, subject started new anticancer treatment, or the subject dies, whichever comes first. The safety reporting periods are defined in Table 8-1.

Trial Period	Reporting Requirements		
Signing of ICF until first dose of trial treatment	AEs, if assessed by the investigator to be caused by a protocol-mandated procedure (eg, tumor biopsy, CT scan), including wash-out or discontinuation of prior medications.		
First dose of trial treatment through SFU2	All AEs and SAEs (see definitions in Appendix 3), regardless of causality, will be documented.		
After SFU2 through end of trial/after end of trial	There is no requirement to monitor subjects for AEs and SAEs following the protocol-required safety reporting periods or after end of trial. However, if the investigator becomes aware of an SAE, it must be reported if judged by the investigator as related to trial treatment.		
Refer to Appendix 3 for additional guidance for recording and reporting AEs and Section 7.1.1 for timing of			

Table 8-1 Reporting Period and Requirements

Refer to Appendix 3 for additional guidance for recording and reporting AEs and Section 7.1.1 for timing of safety follow-up visit(s).

NOTE: Any second primary malignancy(ies) regardless of relatedness to trial treatment, should be reported as an SAE at any time during or after the trial if the investigator becomes aware of such an event (see Section 8.4.3.1). AE=adverse event; CT=computed tomography; ICF=informed consent form; SAE=serious adverse event SFU2=safety follow-up visit 2.

For details regarding follow-up of AEs and SAEs and reporting period for SAEs judged as related to GEN1053 and/or IM, see Section 8.4.6. Refer to Section 6.2 for guidance regarding product complaints.

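### AE, SAE and AESI tables stop 30 days after the last dose although AEs are collected to about day 60, so later-onset events appear only in listings and their incidence may be understated

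*Combined protocol and SAP*

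**What the plan says.** Section 9.4.3.1 divides observation into pretreatment, on-treatment and posttreatment periods. The middle one is the "On-treatment period: from day of first dose of trial medication to 30 days after last dose of trial medication". Two rules follow. First, "Summary tables for AEs will include only AEs that started or preexisting AEs that worsened during the on-treatment period". Second, "SAEs, nonserious AEs, and AESIs during the on-treatment period will be tabulated". Posttreatment AEs, SAEs and AESIs are listed with a flag, and deaths from both periods are summarized. Further AE summaries are left to the SAP. No reason is given for stopping at 30 days.

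Collection runs longer. In Table 8-1 (Section 8.4.2) the full reporting period is "First dose of trial treatment through SFU2", with every AE and SAE documented whether or not it is thought to be related. Collection ends sooner at consent withdrawal, new anticancer treatment or death. Under Section 7.1.1, subjects who stop treatment "will have 2 safety follow-up visits, at 30 days (+5 days) and 60 days", the second with a window of ±7 days. Tables 1-1 and 1-9 schedule hematology, biochemistry and coagulation tests at both visits.

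On holds, Section 6.7.2.1 states: "Administration of trial treatment can be delayed for up to 21 days", longer only with the medical monitor's approval. Section 6.7.2.3 applies the same 21 days after the planned dosing date to thrombocytopenia.

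**The concern.** AEs are a primary endpoint (Table 3-1) of a first-in-human trial, and thrombocytopenia and bleeding are AESIs (Section 8.4.1.1). Section 2.3.2.1 describes thrombocytopenia, bleeding, anemia and "increased plasma levels of ALT, AST, and LDH with delayed onset in monkeys", and Section 8.4.3.5 wants AESIs followed so that the relevance of those findings to humans can be quantified. A listing shows that a late event happened. It does not give an incidence by dose level or expansion cohort, which is what a reader of the safety profile will use.

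The 30-day limit also sits awkwardly with two of the plan's own timings. SFU1 may be held only on or after day 30, so most of its permitted days lie after the tabulation period has closed. And a subject can still be within a permitted dose hold, with the decision to stop not yet made, after day 30. What is at stake is whether the committed AE tables give the full incidence of late toxicity that the trial has already collected.

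**Working it through.** The plan states no figure to reproduce here. The check is date arithmetic on the stated windows, counting days from the last dose.

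**Inputs.** Tabulation ends at day 30 (9.4.3.1). SFU1 is on days 30-35 and SFU2 on days 53-67, nominally 60 (7.1.1). Doses are 21 days apart (6.1). The maximum hold without further approval is 21 days (6.7.2.1).

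**1. Collected but untabulated time after the last dose** = SFU2 day − 30.
- SFU2 at day 53: 53 − 30 = 23 days; 23/53 = 43%.
- SFU2 at day 60: 60 − 30 = 30 days; 30/60 = 50%.
- SFU2 at day 67: 67 − 30 = 37 days; 37/67 = 55%.

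**2. The same gap as a share of all collected time**, by number of doses n, on the nominal schedule with collection to day 60. Collected time = 21(n − 1) + 60; untabulated time = 30.
- n = 1: 30/60 = 50%.
- n = 2: 30/81 = 37%.
- n = 4: 30/123 = 24%.
- n = 9 (about 6 months): 30/228 = 13%.

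**3. SFU1.** Permitted days are 30, 31, 32, 33, 34 and 35. Five of the six fall after tabulation closes. A low platelet count first detected on, say, day 33 would be dated to the posttreatment period. An event reported at that visit with onset by day 30 still counts, because Section 9.4.3.1 goes by start or worsening, not visit date.

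**4. Dose hold.** The next dose is due at day 21 and may be held 21 days more: 21 + 21 = day 42. As an example, suppose thrombocytopenia is found before dosing on day 21, the dose is held, the subject bleeds for the first time on day 36, and dosing never resumes. The thrombocytopenia (onset day 21) is tabulated. The bleed, an AESI, has onset after day 30 and is only listed. Had dosing resumed, the whole hold would have been on-treatment and the bleed would have counted.

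**5. How many events might this be?** The documents give no onset distribution after the last dose. As an assumption only, take exponential onset times with mean m days, truncated at SFU2 day T. The share of post-last-dose events that is untabulated is (e^(−30/m) − e^(−T/m)) / (1 − e^(−T/m)).
- m = 7: about 1% for T = 53 to 67.
- m = 14: 10% to 11%.
- m = 30: 24% to 29%. For T = 60: (0.368 − 0.135)/(1 − 0.135) = 0.27.

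The answer depends almost entirely on m, so the documents do not fix a size.

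**The case against.** The strongest reply is that a collection window and a tabulation window may legitimately differ, and that the plan does not hide late events. This is largely fair. All posttreatment AEs, SAEs and AESIs are listed and flagged, and deaths are summarized. Grade 3 or higher thrombocytopenia and grade 2 or higher bleeding go to the sponsor within 24 hours. The dose escalation and safety committees consider AESIs whenever they occur (Section 8.4.3.5). Safety decisions during the trial do not rest on these tables.

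The evidence for very late toxicity is also thin. Section 2.2.2.1 puts thrombocytopenia in monkeys at 10 to 12 days after the first dose, inside 30 days even for a subject given one dose. The phase 1a signal in Section 2.3.2.1 carries no onset times. Delayed toxicity between cycles stays in the tables; only events more than 30 days after the last dose are affected. The dose-hold case is narrow: it needs a new or worsening event and no redosing. Laboratory tests at the treatment discontinuation visit will catch some abnormalities before SFU1.

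The remaining reply is that the SAP may add summaries. It may, but Section 9.4.3.1 commits to none for the period after day 30, so the gap in the committed tables stands.

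**Conclusion.** The point holds as a reporting gap, not a contradiction. Followed as written, Section 9.4.3.1 leaves every AE, SAE or AESI with onset or worsening after day 30 out of the committed AE incidence tables, although those events are collected and AEs are a primary endpoint. Late-toxicity incidence in those tables may be understated, by an amount the documents do not allow one to estimate.

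Three stronger conclusions might be inferred and are not supported:
- That late toxicity vanishes from all safety output, or that SFU2 contributes nothing beyond deaths. The period restriction sits in the AE section; Section 9.4.3.2 sets no window for laboratory grading, so SFU1 and SFU2 laboratory values are not excluded.
- That the untabulated events fall mainly in subjects who stopped for toxicity. Days 31-60 apply to everyone who stops, including for progression or at their own request, and no breakdown by reason is given.
- That 50%, or 13% to 50% by number of doses, is a share of events lost. These are shares of calendar time and assume collection to day 60. Collection is shorter in subjects who start new anticancer treatment, withdraw consent or die first.

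**What to change.** In Section 9.4.3.1 and the SAP, tabulate TEAEs, SAEs and AESIs from first dose through SFU2 or the end of AE collection, whichever is earlier. Keep the 30-day version alongside, labeled as such, for comparison with other trials. The untabulated stretch then falls to zero on any permitted SFU2 date. Every permitted SFU1 day, and the hold to day 42, lie within the tabulated period unless collection has already ended.

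The change should be made before database lock. It needs no new data, visits or change to patient management. The cost is a short text change and one extra set of tables. The downside is that some late events due to the underlying disease will enter the longer-window tables; the 30-day tables alongside let a reader see how much difference they make.

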9.4.3.2 Clinical Laboratory Tests

Grading of laboratory values will be assigned programmatically as per NCI-CTCAE version 5.0. The calculation of CTCAE grades will be based on the observed laboratory values only, clinical assessments will not be considered.

CTCAE grade 0 will be assigned for all non-missing values not graded as 1 or higher.

9.4.3.3 Other Safety Data (eg, Vital Signs, ECG Parameters)

The following will be provided, as necessary.

- ECOG-PS will be summarized.
- Abnormal findings in physical examinations will be summarized.
- 12-lead ECGs including PR, QRS, QT, heart-rate-corrected QTcF, and RR intervals will be obtained for each subject during the trial. ECG data will be read and interpreted centrally in the Dose Escalation phase only. Any relationship between QTcF and PK concentrations across DLs and time points will be investigated.
- Vital signs data will be tabulated and listed; notable values may be flagged.

9.4.3.4 Patient-Reported Outcomes

Not applicable

9.4.4 *Pharmacokinetic Analyses*

Individual curves of concentration of GEN1053, including information on actual dose, will be presented for all subjects. All available data will be shown in these figures. PK parameters will be calculated based on noncompartmental methods as specified in Table 9-1. These PK parameters will be calculated separately for the Cycle 1 and Cycle 3 administrations. C_{max}, t_{max}, and predose values will be summarized and presented graphically for all trial days where measured.

The relationship between derived PK parameters and covariates such as actual dose, weight, and selected laboratory parameters will be evaluated graphically.

Descriptive statistics of PK endpoints will include arithmetic and geometric means, standard deviation, %CV, median, minimum, and maximum.

Missing concentration values will be reported as is in data listings. Concentration values below LLOQ will be handled as LLOQ/2 in summary statistics and reported as is in data listings. Any missing PK parameter data will not be imputed.

Further exploratory analyses of PK data may be performed.

Table 9-1Noncompartmental Phan	rmacokinetic Parameters
--------------------------------	-------------------------

CL	The total body clearance of drug from the plasma
V	Volume of distribution
t _{1/2}	The elimination half-life associated with the terminal slope (λz) of a semi-
	logarithmic concentration-time curve
C _{max}	The maximum (peak) observed plasma, blood, serum, or other body fluid
	drug concentration after single dose administration
Ctrough	The minimum observed plasma, blood, serum, or other body fluid drug
	concentration prior to the subsequent dose.
t _{max}	The time to reach maximum (peak) plasma, blood, serum, or other body fluid
	drug concentration after single dose administration
AUC _{tau}	The AUC from time zero to day 21 (mass × time × volume -1)
AUC _{last}	The AUC from time zero to last quantifiable measurement

9.4.5 Pharmacodynamic Analyses

Please see Section 9.4.6.

9.4.6 Biomarker Analyses

The exploratory biomarker assessments are intended to evaluate potential pharmacodynamic and safety biomarkers, and to identify markers predictive of response or resistance to GEN1053 as monotherapy or in combination with IM. Since this clinical trial is not designed to test specific biomarker-related statistical hypotheses, the analysis of these data should be viewed as exploratory and hypotheses-generating. Analyses may include how the peripheral T-cell activation and proliferation and cytokine release distribute between the type of responder groups. Descriptive analysis will be performed, and further details for additional analyses will be defined in the SAP. Results from exploratory biomarker assessments may be documented in separate reports.

Biomarkers, including pharmacodynamic markers, may be listed, tabulated, and plotted when deemed appropriate. Analyses may be stratified by clinical covariates or molecular subgroups using the appropriate statistical methods (eg, ANCOVA), proportional hazards regression, or Kaplan-Meier methods) depending on the endpoint and the hypotheses. Baseline biomarker levels or changes in biomarker levels may be assessed for correlation with tumor response and other clinical endpoints to identify responsive or resistant subgroups, as well as biomarkers or pathways attenuated following treatment.

Additional analyses that may be performed after the completion of the end-of-trial CSR will be documented in separate reports. These analyses may include but are not limited to the meta-analysis of data from this trial combined with data from other trials or the analysis of biomarkers

generated from samples collected during the trial but analyzed after the database lock and completion of the CSR. These analyses will be described in an addendum of the SAP, or in a standalone analysis plan document, as appropriate.

Planned analyses are based on the availability of clinically valid assays and may be deferred if emerging trial data show no likelihood of providing useful scientific information.

9.4.7 Immunogenicity Analyses

ADA titers to GEN1053 in monotherapy or in combination therapy will be separately listed and positive/negative host immune response to GEN1053 and presence of neutralizing antibodies may be summarized (positive/negative). The presence of PK concentrations above a certain threshold, which depend on the drug tolerance of the ADA assay at the same time as the ADA sample, may make the ADA undetectable and hence render nonconclusive. The association between positive/non-positive ADA, PK (predose, AUC, C_{max}) and safety findings will be explored.

9.4.8 Health Economics

Not applicable

9.4.9 Multiplicity

There will be no correction for multiple tests.

9.4.10 Subgroup Analyses and Effect of Baseline Factors

To determine whether the treatment effect is consistent across various subgroups, the estimate of the between-group treatment effect (with a nominal 95% CI) for the ORR will be estimated and plotted within each category of the following classification variables (where applicable):

- Age category (eg, <65, ≥ 65 years)
- Sex (female, male)
- Race category (where permitted)
- ECOG status
- Geographic region of enrolling site
- Histology (eg, squamous, nonsquamous)
- Smoking status
- Prior therapy

The consistency of the treatment effect will be assessed descriptively via summary statistics by category for the classification variables listed above.

9.5 Efficacy Monitoring in Expansion Cohorts

The Expansion part will be conducted in at least 2 tumor types using the Bayesian PPoS with a maximum sample size of 40 per indication and treatment (both mono- and combination therapy).

The efficacy in each Expansion cohort will be monitored utilizing the Bayesian efficacy monitoring via predictive probabilities (Lee and Liu, 2008). In particular, the PPoS will be calculated when (at minimum) 2 scans from the first 10 subjects in the Expansion cohort have been locally reviewed. The next futility inspection takes place when data from 20 subjects have been locally reviewed.

At the end of the Expansion cohort, the success criteria are defined as the posterior probability that the confirmed ORR exceeds the ineffective ORR threshold (p_0) with at least 80%. The weights correspond to how likely each outcome is.

If the predicted probability of success is less than 10% the monotherapy Expansion cohort is judged as likely being "futile." However, the threshold of 10% is not considered as a binding futility bar as the Expansion cohort at this stage still is under explorative investigation. The enrollment into the Expansion cohort may also continue (up to maximum 40 subjects) while the scans necessary to derive the response rates in the initial 20 subjects are obtained and reviewed. For the combination therapy Expansion cohort, a 30% threshold determines whether further investigation is judged "futile" or "non-futile." However, again, the criterion is nonbinding.

The ineffective ORR thresholds are tabulated in Table 9-2, with the rates considered to warrant further evaluation of GEN1053 as mono- or combination therapy (p_1) . Based on p_0 , the number of responders required at the monitoring time to consider the data as a likely "success" (by each case) is presented in Table 9-3.

For calculations, the Bayesian Efficacy Monitoring via Predictive Probability application v1.1.4 at www.trialdesign.org has been utilized, based on the following design parameters:

- Beta(p₀,1-p₀) as prior distribution for the response rate
- No early stopping for efficacy

Table 9-2The Ineffective ORR Threshold and the Response Rates That Warrant
Further Evaluation of the Drug

Cancer Type	Case A: Mono Therapy HNSCC	Case B: Combination Therapy NSCLC	
$\begin{array}{l} \text{Ineffective ORR threshold} \\ (\text{ORR} \leq p_0) \end{array}$	p ₀ =10%	p ₀ =15%	
ORR that warrants further evaluation of the drug	p1=25%	p1=30%	

HNSCC=head and neck squamous cell carcinoma; NSCLC=non-small cell lung cancer; ORR=objective response rate

Table 9-3Number of Responders Required at Monitoring Time to Consider Data
as a Likely "Success" (by Each Case)

Case	Data Likely Non-futile at 10 Subjects' Monitoring Time	Data Likely Non-futile at 20 Subjects' Monitoring Time	Number of Responses Required to Meet Success Criteria in 40 Subjects	True ORR	Likelihood to Consider Data Futile at any Interim	Likelihood to Meet Success Criteria at Final Analysis
A N/A	≥2/20	≥6/40	10%	48%	17%	
			25%	7%	91%	
B ≥2/10	>4/20	>9/40	15%	72%	10%	
	≥2/10	≥4/20	≥ 9/40	30%	19%	76%

ORR=objective response rate

Prior distributions: A beta (0.1, 0.9); B beta (0.15, 0.85)

